8.8 Reporting Deviation from the Original Statistical Plan

The statistical analysis plan needs to be confirmed by the sponsor and the main investigator, and to be finalized before the locking of database. Prior to finalization, adjustments could be made on the initial analysis plan according to the actual situation during clinical trials. In principle, the main analytical principles, methods, and analysis set will not be modified, and all adjustments will be recorded.

8.9 Standards and Reasons for Selecting Subjects to be included in the Analysis

Statistical analysis will be performed upon the following demographics, demographic categorization will be done prior to the statistical analysis, the analysis population in this clinical trial includes:

Full Analysis Set (FAS): collection of subjects selected based on the Intention To Diagnostic (ITD) principles, refers to the dataset of all subjects who participated in the research and used the investigational device.

Per Protocol Set (PPS): the subgroup of the subjects who completed the trial, excluding those who seriously violated the procedure (refers to the trial subjects who violated the selection standard or the exclusion standard, or those lost during the trial).

Safety Set (SS): Use the same definition method as the Full Analysis Set (FAS), therefore the Safety Set will not be defined separately in the analysis.

The analysis of primary efficacy index will be performed on the Full Analysis Set (FAS) and the Per Protocol Set (PPS); in addition, all baseline demographic data and secondary efficacy analysis will be performed on the Full Analysis Set (FAS), the safety evaluation will also be performed on the Full Analysis Set (FAS).

8.10 Exclusion of Special Information during Hypothesis Verification and Its Reasons (If Applicable)

Not applicable.

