7.1 Trial Design

This study is multi-center, prospective, single-subject design clinical trial. Subjects that signed Informed Consent form (ICF) which was approved by the Ethics Committee (EC) will enter selection process. Subjects that meet all inclusion criteria and do not meet any of the exclusion criteria, are considered eligible to enroll in the clinical trial.

Coronary angiography is performed on subjects. The investigators combine angiographic images and subject's inclusion/exclusion criteria to confirm if the subject meets the trial requirements. The subjects who met the criteria for this study will be registered by login to the central registration system after enrollment, and the investigational device will first be used to measure the fractional flow reserve of coronary stenosis lesions, and then the measurement of the same lesions by using the control device will be recorded, and followed with a 48hr post operation follow-up. The investigational device measure FFR using the innovative 1-sensor method according to the product Instructions for Use (IFU), and the control device measure FFR through the conventional AO method according to the product Instructions for Use (IFU).

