8.1.2 Statistical Analysis Methods

(1) Descriptive Analysis: Describing qualitative data with frequency and composition ratio description; describing quantitative data with mean, standard deviation, maximum, minimum, median, interquartile range, 25th percentile, and 75th percentile.

(2) Baseline demographics statistical analysis: Mainly based on descriptive analysis, comparing subgroups that may be involved, use likelihood ratio χ^2 test between qualitative groups, use Fisher' s exact test when more than 25% of cell frequencies are less than 5; conduct group T-test between normally distributed quantitative datasets; apply Wilcoxon Rank Sum test between non-normally distributed quantitative datasets.

(3) Efficacy analysis: All subjects undergoing a study product review will be included in the analysis (according to the Intention To Diagnostic (ITD)), for the primary efficacy index, in addition to the point estimate for coronary heart disease diagnosis accuracy, the asymptotic normal method and the exact probability method would also be used to make estimates in the 95% confidence interval, comparing the lower bound of the confidence interval with a target value to determine whether the investigational device satisfies clinical application requirements.

(4) Safety evaluation: Adverse events are described by the number and frequency of adverse events; meanwhile, the specific performance, the severity, and the relationship with investigational device of all adverse events will be described in detail.

(5) For primary evaluation indicators, statistical analysis will be conducted with a one-tailed 0.025 significance level, other indicator statistical analysis will be conducted with a two-tailed 0.05 significance level (unless stated otherwise). Statistical analysis is done with SAS®9.4 statistics software.

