8.4 Expected Drop Out Rate

In the sample size design process, the maximum drop out rate during the clinical trial is expected to be 10%, such drop out rate includes all reasons that prevent a subject from being selected for primary analysis, usually referred to serious violations of clinical trial protocols as determined by researchers (influencing the primary efficacy analysis). Possible scenarios include: a subject does not meet the inclusion criteria, or meets the exclusion criteria; a subject did not use any test-related products; a subject used third-party products outside of clinical trial or such. All of the above will be included in the total drop out rate.

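### Section 8.9 limits the Full Analysis Set and Safety Set to subjects who used the investigational device without defining use, so device failures before insertion can drop out of the primary endpoint and the device success rate

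*Combined protocol and SAP*

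**What the plan says.** **Analysis sets (8.9).** The FAS is said to follow the Intention To Diagnostic principle and "refers to the dataset of all subjects who participated in the research and used the investigational device". For the Safety Set the instruction is: "Use the same definition method as the Full Analysis Set (FAS), therefore the Safety Set will not be defined separately in the analysis". The primary endpoint is analysed on the FAS and the Per Protocol Set. Secondary efficacy, which includes device success, and safety are analysed on the FAS. The Per Protocol Set takes subjects who completed the trial, so it does not bring back anyone missing from the FAS.

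**Order of events (7.1, 7.1.4).** Eligible subjects are "registered by login to the central registration system after enrollment, and the investigational device will first be used to" measure FFR, with the control wire second. The 1-sensor directions in 7.1.4 start with opening the package. Soaking and calibration, connection to the handle, a connection check, zeroing and removal from the coil all come before insertion. Removal carries a warning about damage, and 6.3 says that a damaged wire must not be used.

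**Text that leans towards inclusion.** Section 8.1.2 says "All subjects undergoing a study product review will be included in the analysis", again under Intention To Diagnostic, but does not explain the phrase. Section 8.7 scores missing primary results as inconsistent and keeps withdrawn subjects in the analysis.

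**Device success (7.1.6, 7.2.1.2).** Success is an effective FFR reading, judged per vessel.

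**The concern.** Entry to the FAS depends on an event after registration, and the performance of the investigational device can decide that event. This does not fit the Intention To Diagnostic label. If a wire fails at calibration, at connection or through damage on removal, and no investigational reading is obtained, the literal text of 8.9 removes the subject before 8.7 can score the missing result as inconsistent. The same step takes a plain device failure out of the success-rate denominator.

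Removing such subjects can only raise the observed agreement and the observed success rate. The trial is decided by comparing a lower confidence bound with 75% (8.5), so a few such subjects could matter. Because *used* is undefined, the decision on whether they belong could be taken after the failures are known.

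**Working it through.** **Inputs from the documents.** Expected agreement 83%, target 75%, one-sided 0.025, 300 subjects, drop-out up to 10% (8.2.1); power about 90% (8.3); pass if the lower 95% bound exceeds 75% (8.5). Section 8.1.2 names both an asymptotic and an exact interval; the exact (Clopper-Pearson) bound is used here.

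**Step 1: reproduce the plan's power.** From the formula in 8.2.1, power = Φ{[(0.83 − 0.75)√n − 1.96√(0.75×0.25)] / √(0.83×0.17)}.
- n = 300: (1.3856 − 0.8487)/0.3756 = 1.429, power 92.4% (exact 92.6%).
- n = 270, after 10% drop-out: (1.3145 − 0.8487)/0.3756 = 1.240, power 89.3% (exact 88.9%).

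This agrees with the stated power of about 90%.

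**Step 2: exclude or count pre-use failures.** Assumptions, neither from the documents: k = 300f registered subjects have a pre-use failure with no investigational reading, and agreement is 83% among the other n = 300 − k.
- Excluded: pass if the number consistent among n reaches the exact-bound minimum for n.
- Counted as inconsistent: expected rate is 0.83(1 − f), and at least 240 of 300 must be consistent, all coming from the n users.

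| f | k | n | Minimum to pass, of n | P(pass), excluded | Expected rate, counted | P(pass), counted |
|---|---|---|---|---|---|---|
| 0 | 0 | 300 | 240 | 92.6% | 83.0% | 92.6% |
| 1% | 3 | 297 | 238 | 91.6% | 82.2% | 86.0% |
| 2% | 6 | 294 | 236 | 90.5% | 81.3% | 76.1% |
| 3% | 9 | 291 | 233 | 91.8% | 80.5% | 63.0% |
| 5% | 15 | 285 | 229 | 89.6% | 78.9% | 32.6% |

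The small rises and falls in the excluded column come from the discreteness of the binomial. When failures are excluded, the expected reported rate stays at 83% throughout.

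**Step 3: when the result changes.** With about 83% observed among users, 12 failures (12/300 = 4%) are enough. 239/288 has a lower bound of 78.1% and passes; 239/300 = 79.7% has a lower bound of 74.7% and fails. With 11 failures, 240/300 still passes, at 75.02%.

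**Step 4: false-pass probability.** Suppose true agreement, with failures counted, is exactly 75%. Agreement among users is then 0.75/(1 − f). With failures counted, P(pass) is 2.5% (240 of 300). With failures excluded:

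| f | Agreement among users | P(pass) |
|---|---|---|
| 1% | 75.8% | 4.3% |
| 2% | 76.5% | 7.2% |
| 3% | 77.3% | 14.6% |
| 5% | 78.9% | 30.9% |

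**Step 5: the other reading of 83%.** If 83% already counts failures, power with failures counted is the 92.6% of step 1, so the loss in step 2 does not arise. Exclusion would still lift the expected estimate to 0.83/(1 − f): 83.8%, 84.7%, 85.6% and 87.4% at 1, 2, 3 and 5%.

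**The case against.** The strongest reply is that *used* may already cover these subjects. The 7.1.4 directions for using the system begin at opening the package, so a wire that fails at calibration could be said to have been used; the subject would be in the FAS and scored inconsistent. Section 6.3 points the other way, since it places inspection before use and bars use of a damaged wire. Sections 8.1.2 and 8.7 also lean towards inclusion. This stands as far as it goes: the text is ambiguous and does not plainly exclude every such failure. But neither section overrides 8.9, and the ambiguity is itself the defect.

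The reply on size also stands in part. The failure rates are assumed, and 8.2.1 does not say that 83% is conditional on use.

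A reader might infer four stronger points that the documents do not support:

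- *Adverse events in control-only subjects are lost.* They are not. Sections 7.2.1.2, 13.3 and 13.4 require events and device defects to be recorded, and serious events to be reported. The events would lie outside the defined analysis set; they would still be collected.
- *Section 8.4 confirms the exclusion.* Its drop-out example is "a subject did not use any test-related products". A subject measured with the control wire has used such a product, so the clause does not reach this case.
- *A failed preparation leads straight to the control wire.* No section says so. Section 7.1.4 gives recalibration and reset procedures, and the documents are silent on a replacement wire. If a second investigational wire is used, the subject is in the FAS.
- *The plan as a whole is tilted towards the device.* This is not shown. Failures after insertion stay in the FAS and count as inconsistent, and so does a missing control reading after an investigational one.

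**Conclusion.** The concern holds as a gap in the definition of the analysis sets. On the literal wording of 8.9, a registered subject with a pre-insertion device failure and no investigational reading is outside the FAS and the Safety Set, and so outside the primary, device-success and safety analyses.

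The size depends on a failure rate that the documents do not give. At 1% the effect on the probability of passing is modest (92% against 86%). At 3 to 5% it is large (92% against 63%, and 90% against 33%). These differences assume 83% agreement among users. The false-pass figures do not rest on that assumption, but they do rest on the failure rate. If no pre-use failure occurs, nothing changes. The documents do not show that the pass/fail decision will be wrong; they leave open a route by which it could be.

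**What to change.** In 8.9, define the FAS as all centrally registered subjects in whom FFR measurement with the investigational device was intended. State that an absent investigational reading for any device reason, including before insertion, is scored inconsistent under 8.7 and counted as an investigational-device failure in the success rate. Align the population wording in 8.1.2 with this definition. Section 8.4 needs no change on this account.

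Define the Safety Set separately as subjects exposed to either study device or to the study hyperaemic drug, so that events already recorded for control-only subjects fall in a defined analysis set.

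The cost is wording in 8.1.2, 8.9 and the analysis plan; the registration data needed already exist. The downside is slightly lower agreement and success rates if pre-use failures occur. Section 8.8 says that the analysis sets will in principle not be modified later, so the change should be made now, before any failures are known.

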9 DATA MANAGEMENT

The collection of clinical data was done by using an Electronic Data Capture (EDC) system. The EDC system has undergone rigorous testing and fully meets the requirements of "Good Clinical Practice for Medical Device" and "Clinical Trial Data Management Technical Guidelines". Before the system is officially launched, it is necessary to conduct training tests on relevant users to ensure that the system meets the test requirements. After the official launch, the relevant personnel will get the account number and password. The account is bound to the user's role and permissions. The account information must be properly kept. The account information must not be shared with others or exercise tasks for others.

9.1 DATA COLLECTION

EDC transfers data directly from the client terminal to the server side over the Internet. Without filling out a paper case report form, investigators can complete data collection by entering the source data directly into the EDC system. Investigators are responsible for the quality of the data entered to ensure the authenticity and integrity of the data. The EDC system provides interface printing, allowing investigators to print information on electronic case reports as needed.

9.2 DATA VERIFICATION AND MODIFICATION

The EDC system provides both online and offline verification methods. When the investigator enters abnormal data, the EDC system issues a real-time warning to remind the investigator to check the data. The data administrator performs a logical check on the data held by the server and issues the wrong data in the form of manual challenge through EDC. Investigators need to answer questions posted. The auditor needs to periodically remind and assist the investigator to answer the questions and ensure that each question is handled correctly. The system will record all the questions and the corresponding answers.

9.3 DATABASE LOCK

When all data entry is completed and submitted, all questions are answered, the system enters the soft lock state. The statistician will generate a blind audit report based on this database. If the confirmation data requires no more modified, the sponsor, the data management person in charge, and the statistical person in charge must sign the database lockout form, and the data administrator will complete the database lock operation according to this form. The locked database must not be modified again. If there is an error affecting the main efficacy index or safety indicator, the sponsor, the data management person in charge, and the statistical person in charge must confirm the unlocking

modification and sign the database unlocking form. The data administrator will modify the error data and perform quality control according to the reason of the unlocking. After the error is revised, the sponsor, the data management person in charge, and the statistical person in charge are required to sign the database lockup form again.

10 FEASIBILITY ANALYSIS

10.1 PROBABILITY OF SUCCESS ANALYSIS

A series of tests and researches have been carried out during the development of this product, including laboratory bench tests, animal studies, and human factors research etc. The company has established a strict quality system, established design control procedures for design and development, and formed documents to implement planning and control of the product design and development process. The product has passed the type testing of Shanghai Medical Device Quality Supervision and Inspection Center of the China Food and Drug Administration (CFDA) and has been strictly tested before leaving the factory. There will be no defective products. In addition, the control device has been approved for marketing in the country. In this trial, the investigator will enroll subjects who meet the trial requirements based on the indication for use of the investigational device. The study design meets CFDA requirements.

10.2 PROBABILITY OF FAILURE ANALYSIS

The main causes of treatment failure or poor performance may be related to the following factors: 1) accuracy and proficiency of the operation; 2) inaccurate understanding of indications for use and contraindications; 3) product defects specifically due to manufacturing.

In addition to the above reasons, there may be other unpredictable risks (such as wire breakage) in this trial, leading to trial failure. However, by following this protocol, conduct procedure at a trial institution, adhering to the subjects' inclusion criteria, and closely monitoring the physical condition of the subjects during the procedure can minimize the risk.

11 QUALITY CONTROL OF CLINICAL TRIALS

During the trial, sponsor assigned auditors will conduct on-site audit to ensure that all aspects of the protocol are strictly followed, and trial documents are filled out correctly. Investigators must undergo unified training so to perform recording and judgment criteria with consistency. The entire trial should be carried out under strict operational standard. The investigator should fill in the requirements

according to the medical report form, truthfully, in detail, and carefully record the contents of the EDC to ensure that the case report form is complete, true and reliable. All observations and findings in clinical trials should be verified to ensure data reliability and to ensure that conclusions from clinical trials are derived from raw data. There are corresponding data management measures in the clinical trial and data processing stages.

The original information from this trial, including signed informed consent, products distribution records, relevant laboratory inspection reports, auxiliary examination reports, case records and other relevant records, shall be kept at the investigational site's related hospital for 10 years after the end of the clinical trial. The Sponsor shall keep the clinical trial data until this product is no longer on the market.

12 ETHICAL ISSUES AND INFORMED CONSENT IN CLINICAL TRIALS

12.1 ETHICAL CONSIDERATIONS

This clinical trial complies with the requirements of the Helsinki Declaration of the World Medical Assembly and relevant Chinese regulations, and shall, in accordance with the requirements of the CFDA Order No.25, pass the ethical audit of the investigational site and protect the rights of the subjects of the clinical trial in accordance with the ethical principles stipulated therein, safety and health, as well as privacy.

12.2 REVIEW AND APPROVAL OF THE TRIAL PROTOCOL

Clinical trial protocol must be submitted to the medical Ethics Committee of the investigational site hospital for approval prior to initiate the clinical trial. During the clinical trials, if the protocol is revised, it shall be implemented only after obtaining written approval from the Ethics Committee.

12.3 INFORMED CONSENT PROCESS AND INFORMED CONSENT FORM

The Ethics Committee must approve the drafted ICF. The sponsor provides ICF to each investigational site. To meet specific requirements, the investigational site may modify ICF. Each investigational sites present sponsor with a copy of the ICF approved by the Ethics Committee, as well as a copy of the renewal and permission for the duration of the trial. The original signed and dated ICF by subject is kept by the investigational site for audit and a copy will be given to the subject.

Whenever new information that may affect the patient's consent is obtained,

ICF (and any other written information provided to the subject) is updated. Any such amendments or updates must be reviewed and approved by the Ethics Committee before made available to the subjects.

13 PROVISIONS ON ADVERSE EVENTS AND DEVICE DEFECTS

REPORTING

13.1 ADVERSE EVENTS

Definition: Adverse Events (AE), are adverse medical events that occur during clinical trials, whether or not is related to investigational devices.

Grade:

Mild: Subject can tolerate, does not affect diagnosis and treatment, do not requires special treatment, no impact on the subject's health.

Medium: Subject can not tolerate, and requires special treatment, direct impact on the subject's health.

Severe: Endangers subject's life, results in death or disability, requires emergency treatment.

13.2 SERIOUS ADVERSE EVENTS

A serious adverse event is a death or serious deterioration of health during a clinical trial, including a fatal illness or injury, a permanent defect in the body's structure or function, a need for hospitalization or prolonged hospitalization (Except for those who are hospitalized for medical insurance reimbursement, elective surgery, routine treatment of the disease under study or previous diseases without deterioration of the condition, and who are not hospitalized for emergency treatment only, they are recorded in the original medical case report, and no serious adverse events are reported.), medical or surgical intervention to avoid permanent defects in the body structure or physical function; causes fetal distress, fetal death or congenital abnormalities, congenital defects and other events.

13.3 DEVICE DEFECTS

Device defects refer to under normal use of medical device presents the unreasonable risks that may endanger health and life, such as mislabeling, quality problems, malfunctions and so on.

The investigator shall record all adverse events and device defects during the clinical trial, and jointly analyze the causes of the events with sponsor, form a written analysis report includes opinions on continuing, suspending or terminating the trial, The report shall be submitted by the medical device clinical trial management department of the investigational site to its Ethics Committee for review.

